Several trials compared a single-inhaler fixed dose combination (FDC) TT with an open combination of TT (ICS/LABA plus LAMA) respectively and found a small degree of greater benefit with FDC TT.⁸ Several Randomized Controlled Trials (RCTs) assessing the comparison of DBT LAMA-LABA to TT FDC of LAMA-LABA-ICS inhalers reported fewer exacerbations over one year with TT FDC. 9,10,11 However, these findings are complicated by methodologic issues related to the withdrawal of maintenance treatment at randomization, inclusion of patients with history of asthma and around at least 40% -70% utilizing ICS before entering the clinical trials. $\frac{12,13,14}{12}$ TT is associated with 53% greater risk of pneumonia compared to DBT and is frequently used inappropriately, including overuse in certain COPD patients. 15,16,17,18,19 Approximately 13% -15% of maintenance treatment naïve patients are prescribed FDC TT as first line long-acting maintenance medication (Data on File) contradicting guideline recommendations and irrespective of the safety concerns. We believe a major reason of that practice pattern is just out of convenience as FDC TT are now available in the market. and certain pharmaceutical companies are encouraging early prescribing of triple therapy, including amongst primary care physicians. Any deviation in pharmacological management, particularly maintenance treatment initiation of COPD patients that is different from GOLD 2020 or ATS 2020 strategy document for the management of COPD may have both clinical and economic consequences.²⁰

Given the high-cost side effect associated with long-term use of ICS and inconsistent evidence concerning whether there is a clinically relevant benefit of ICS combination therapy in terms of COPD disease control, it is important to assess differences between subsets of COPD patients in terms of the effectiveness and cost of FDC TT versus other non-ICS options, such as FDC DBT (e.g., Tiotropium+Olodaterol).

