9.1 STUDY DESIGN

This is a non-interventional study with existing data. It will be a retrospective, observational, non-interventional, new user design, real world study of Commercial Insurance and Medicare beneficiaries, using administrative claims data for the period of 15th September 2016 through 31st March 2020.

Patients initiating Stiolto, or Trelegy will be identified using pharmacy claims database). The date of the first prescription claim (on or after 15th September 2017) will be defined as the index date. Patients will be required to have a diagnosis of COPD (ICD-9-CM: 491.xx, 492.xx, 496.xx; ICD-10-CM: J41-J44) on two separate medical claims. Patients 40 years or older will be included in the study. Patients will be required to have continuous enrolment for 12 months prior to the index date. Patients will be excluded if they show any

Proprietary confidential information © 2022 Boehringer Ingelheim International GmbH or one or more of its affiliated companies

use of COPD maintenance medications (ICS, LABA or LAMA in any combination), during the baseline period of six months pre-index date. This will satisfy the criteria for being considered as treatment naive. Patients with two separate medical claims with a diagnosis of asthma, lung cancer, interstitial lung disease, or cystic fibrosis during the study period will be excluded. Using propensity score matching (PSM) technique, we will develop matched cohorts of patients between Stiolto initiators and Trelegy initiators. We will conduct 1:1 matching using nearest neighbour matching approach with a caliper of 0.2. Exacerbation will be defined as a COPD hospitalization (severe exacerbation) or Emergency Department (ED) visit (severe exacerbation) with COPD, or use of approved respiratory antibiotics (e.g., Azithromycin) \pm Oral CorticoSteroids (OCS) medications within \pm 7 days of the office/outpatient visit (moderate exacerbation) as the primary diagnosis. Multiple exacerbations occurring within 14 days of each other will be considered as a single exacerbation and will be per the higher severity. A schematic of the study design is presented below in Figure 1.

Boehringer Ingelheim Non-Interventional Study (NIS) Protocol BI Study Number 1237-0121

c38026921-01

Proprietary confidential information © 2022 Boehringer Ingelheim International GmbH or one or more of its affiliated companies

Figure 1 Study Design

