9.3 VARIABLES

The definitions for exacerbations are as below.

- A severe exacerbation will be defined as follows:
 - An inpatient admission or an ER visit with a COPD diagnosis code in the primary position; or
 - An inpatient admission or an ER visit with a diagnosis code for acute respiratory failure in the primary position and a COPD diagnosis code in any position; or
 - An inpatient admission or an ER visit with a diagnosis code for acute respiratory failure in the primary position + an inpatient admission or an ER visit within ±7 days with a COPD diagnosis code in any position.
- A moderate exacerbation will be defined as follows:
 - An ambulatory (office or outpatient) visits with a COPD diagnosis code in any position + a pharmacy claim for an oral corticosteroid (OCS) prescription within ±7 days of the office/outpatient visit; or

Proprietary confidential information © 2022 Boehringer Ingelheim International GmbH or one or more of its affiliated companies

- \circ An office or outpatient visit with a COPD diagnosis code in any position + a pharmacy claim for respiratory antibiotic prescription within ±7 days of the office/outpatient visit; or
- An office or outpatient visit with a COPD diagnosis code in any position + a pharmacy claim for an OCS + a pharmacy claim for respiratory antibiotic prescription within ±7 days of the office/outpatient visit.
- Pneumonia diagnosis: Binary indicators will be created to identify patients with a diagnosis of 1) pneumonia (Appendix 1). The time to first pneumonia diagnosis, and time to first pneumonia, during follow-up will also be captured.
- Pneumonia-related hospitalization: Binary indicators will be created to identify
 patients with an acute hospitalization with diagnosis of 1) pneumonia in any
 position (Appendix 1) The time to first pneumonia-related hospitalization during
 follow-up will also be captured.
- COPD exacerbation and/or pneumonia diagnosis: Binary indicators will be created to identify patients with each of the following composite outcomes: severe COPD exacerbation or an acute hospitalization with a diagnosis of pneumonia in any position, severe COPD exacerbation or a hospitalization with a diagnosis of pneumonia in any position, any COPD exacerbation or pneumonia diagnosis in any position, and any COPD exacerbation or pneumonia diagnosis in any position. Time to event variables will be created for each composite outcome during the follow-up period.

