9.3.2 Outcomes

9.3.2.1 Primary Outcomes

The primary outcome event for effectiveness is time to first COPD exacerbation after cohort entry. The event is defined as follows:

- Severe exacerbation:
 - Hospitalization with a principal discharge diagnosis of COPD and/or
 - An emergency department (ED) visit with a discharge diagnosis of COPD
 - An inpatient admission or an ER visit with a diagnosis code for acute respiratory failure in the primary position and a COPD diagnosis code in any position
- Moderate exacerbation:
 - \circ An antibiotic for a respiratory condition dispensed \pm an OCS

Time to the first COPD exacerbation will be measured from index date until the occurrence of a hospitalization for COPD (severe exacerbation) or ED visit for COPD (severe exacerbation) or prescription of an antibiotic \pm an OCS on the same day (moderate exacerbation). Severe and moderate exacerbations were considered as a composite for main analyses. Sensitivity analyses will include stratification by exacerbation severity.

Exacerbations will be categorized as moderate or severe and a count of any (severe or moderate), severe, and moderate will be provided.

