9.5 STUDY SIZE

Considering the study design being non-interventional study with existing data, retrospective, new user design and treatments being: Stiolto Respimat (active treatment) vs. Trelegy Ellipta (comparator), primary endpoint of time to first exacerbation (moderate/severe) and COPD population being maintenance treatment naïve, we didn't find any such study that exactly matches these criteria in literature.

We looked at two retrospective, observational, non-interventional studies in the literature. Suissa et al published in Chest (CHEST 2020; 157(4):846-855) a real-world study of COPD treatment, the triple combination of LAMA, LABA, and ICS inhalers and compared its effectiveness to combining LAMA and LABA inhalers in preventing COPD exacerbations.²³ Suissa et al had a sample size of ~2000 patients on LAMA and LABA.²³ They reported that the adjusted hazard ratio (HR) of a COPD exacerbation associated with LAMA-LABA-ICS initiation compared with LAMA-LABA initiation was 0.97 (95% CI, 0.87-1.08). For patients with blood eosinophil counts > 6%, the HR was 0.66 (95% CI, 0.46- 0.94). For patients with two or more prior exacerbations, it was 0.83 (95% CI, 0.70-0.98). ²⁹ The incidence of severe pneumonia requiring hospitalization was increased with LAMA-LABA-ICS initiation (HR, 1.46; 95% CI, 1.03-2.06). ²⁹ The second study, by Palli et al compared health plan-paid costs, COPD exacerbations, and pneumonia diagnoses among patients newly treated with a LAMA + LABA regimen composed of tiotropium (TIO) + olodaterol (OLO) in a fixed-dose combination inhaler (TIO + OLO) or TT in a U.S. Medicare Advantage Part D insured population.²⁴ This study was published in Journal of Managed Care & Specialty Pharmacy 2020 26:10, 1363-1374 and had a sample size of ~1500 patients on Stiolto.³⁰ Palli et al reported longer time to first severe COPD exacerbation (P = 0.020) and first pneumonia diagnosis (P = 0.002) for TIO + OLO versus TT and a lower percentage of TIO + OLO patients experiencing these events (severe COPD exacerbation: 9.0% vs. 16.1%; pneumonia: 14.5% vs. 19.3%).³⁰

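### Pneumonia can count as a primary-endpoint exacerbation, which tilts the hazard ratio towards Stiolto by an unknown amount, and no planned analysis removes it

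*Combined protocol and SAP*

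**What the plan says.** The combined protocol and SAP defines the exacerbation endpoint in four places, and they do not agree.

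- Section 9.3 accepts, among other routes to a moderate event, "An office or outpatient visit with a COPD diagnosis code in any position + a pharmacy claim for respiratory antibiotic prescription" filled within ±7 days. No oral corticosteroid is needed on this route.
- Section 9.3.2.1, which defines the primary outcome, needs only "An antibiotic for a respiratory condition dispensed", with or without an oral corticosteroid. It states neither a visit nor a COPD code.
- Sections 9.1 and 9.2.2 describe the antibiotic-plus-visit event and close with "moderate exacerbation) as the primary diagnosis".
- Severe events in 9.3 and 9.3.2.1 include "An inpatient admission or an ER visit with a diagnosis code for acute respiratory failure in the primary position and a COPD diagnosis code", wherever the COPD code stands on the claim.

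Both grades enter the primary analysis: "Severe and moderate exacerbations were considered as a composite for main analyses". Pneumonia is a separate objective, with hospitalized pneumonia as the secondary outcome (9.3.2.2). Section 7 gives the expected direction: "TT is associated with 53% greater risk of pneumonia compared to DBT".

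Only one planned sensitivity analysis bears on event type: "Sensitivity analyses will include stratification by exacerbation severity".

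**The concern.** Exacerbation is the effectiveness question and pneumonia is the inhaled-corticosteroid harm question, yet one claim can answer both. A patient seen in the office with pneumonia coded first and COPD second, who fills azithromycin, has a moderate exacerbation under 9.3 and 9.3.2.1. An admission with respiratory failure as the primary diagnosis, and COPD and pneumonia also coded, is a severe exacerbation. It also meets the 9.3 rule for a pneumonia-related hospitalization, which takes pneumonia in any position.

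This is not misclassification that can be assumed equal in the two arms. The protocol expects more pneumonia on the comparator, so the excess that reaches the endpoint pulls the primary hazard ratio towards Stiolto. A modest result in that direction could not be read as effectiveness alone. The same excess could then appear again in the secondary result, so the two findings would not be independent evidence.

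**Working it through.** **1. Which events count, by section**

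| Claim pattern | 9.1 / 9.2.2 | 9.3 | 9.3.2.1 |
|---|---|---|---|
| Office visit, pneumonia first, COPD second, antibiotic | No, if COPD must be primary | Moderate | Moderate |
| Office visit, COPD first, pneumonia second, antibiotic | Moderate | Moderate | Moderate |
| Respiratory antibiotic fill, no COPD-coded visit | No | No | Moderate |
| Admission, respiratory failure primary, COPD and pneumonia secondary | Unclear | Severe | Severe |
| ED visit, pneumonia first, COPD second | Unclear | No | Severe, if any position is allowed |
| Admission, pneumonia primary, COPD secondary | Unclear | Not by itself | Not by itself |

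The second row counts under every version, so the primary-diagnosis wording narrows the leak without closing it.

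**2. Existing safeguards**

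- The severity split leaves the whole antibiotic route in the moderate stratum and respiratory-failure stays in the severe stratum.
- The composites in 9.3 add pneumonia to exacerbation.
- Matching on baseline pneumonia (9.3.3) concerns events before the index date.
- Section 9.9 mentions outcome misclassification and unspecified bias analysis, without naming pneumonia.

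**3. Size of the shift**

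The plan has no figure of its own to reproduce here. Two pneumonia ratios R (triple/dual) can be drawn from it:

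- R = 1.53, reading the 53% greater risk in section 7 as a hazard ratio.
- R = ln(1 − 0.193) / ln(1 − 0.145) = 0.2144 / 0.1567 = 1.37, from the 14.5% and 19.3% in section 9.5.

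Let p be the share of Stiolto-arm qualifying events that are pneumonia, and set the true exacerbation hazard ratio to 1. Then HR (Stiolto/Trelegy) = 1 / (1 + (R − 1)p).

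| p (assumed) | R = 1.37 | R = 1.53 |
|---|---|---|
| 5% | 1/1.0185 = 0.98 | 1/1.0265 = 0.97 |
| 10% | 1/1.037 = 0.96 | 1/1.053 = 0.95 |
| 20% | 1/1.074 = 0.93 | 1/1.106 = 0.90 |

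**4. What that does to the test**

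Take 3018 patients per arm (9.5), two-sided 0.05 (assumed), pneumonia 14.5% vs 19.3%, and an assumed 30% with a true exacerbation. Let f be the assumed fraction of pneumonia hazard counted as exacerbation. With H = −ln(1 − proportion), HR = (0.3567 + 0.1567f) / (0.3567 + 0.2144f).

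| f | p implied | HR | Events | Chance of a significant Stiolto advantage (nominal 2.5%) |
|---|---|---|---|---|
| 10% | 4% | 0.985 | 1888 | 5% |
| 25% | 10% | 0.965 | 2002 | 12% |
| 50% | 18% | 0.938 | 2185 | 32% |

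Varying the exacerbation share from 20% to 50%, f = 10% gives HR 0.976–0.992 and a chance of 4–6%; f = 25–50% gives HR 0.913–0.981 and 8–46%.

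**5. If triple therapy truly helps**

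Section 9.5 cites 0.83 (triple/dual) for patients with two or more prior exacerbations, which is 1/0.83 = 1.20 as Stiolto/Trelegy. Using that for illustration, with the same 30% and f = 50%, the observed value is 0.4350 / (0.83 × 0.3567 + 0.1072) = 1.08. Power to detect the Trelegy benefit falls from 97% to 41%.

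**The case against.** Several points on the other side stand.

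- The documents give neither p nor f. The 14.5% and 19.3% are patients with any pneumonia diagnosis, not the share of first exacerbations that are pneumonia, so they do not establish p. At low leakage the shift is about 1–2%.
- Only the between-arm excess shifts the ratio. In a time-to-first analysis, pneumonia after a counted exacerbation has no effect. The arithmetic treats the two events as independent; overlap would reduce the shift.
- A pneumonia-primary admission is not by itself a severe exacerbation. A reader might infer that the cited hospitalized-pneumonia hazard ratio of 1.46 applies to this endpoint. It does not carry over to the outpatient antibiotic route.
- A reader might set the cited overall exacerbation result of 0.97 beside the ratios above and conclude that the artefact exceeds a known effect in the same direction. That 0.97 is triple versus dual, about 1/0.97 = 1.03 on the Stiolto/Trelegy scale, so it points the other way.
- A severe-only analysis does remove the antibiotic route, which is the main one.
- Excluding pneumonia-coded events conditions on a post-index diagnosis that treatment may affect. True exacerbations with concurrent pneumonia would be dropped, more often in the Trelegy arm, which could over-correct.

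These points limit the size and argue against replacing the endpoint. They do not answer the gap: no planned analysis isolates the pneumonia contribution.

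**Conclusion.** The concern holds for mechanism and direction. Under 9.3 and 9.3.2.1 some pneumonia counts as exacerbation, the protocol expects more of it on Trelegy, and nothing planned takes it out. The size is conditional: an expected hazard ratio of 0.97–0.98, 0.95–0.96 or 0.90–0.93 at an assumed p of 5%, 10% or 20%, given no true effect, R of 1.37 to 1.53, and no overlap between pneumonia and exacerbation.

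A reader might infer that any Stiolto advantage will be false, or that the primary endpoint must be redefined. The documents support neither. The leaked share is unknown, the definitions conflict on how wide the route is, and with a true Trelegy benefit the effect would be masking. What is supported is a cheap, prespecified check that lets the main result be interpreted.

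**What to change.** 1. Reconcile the exacerbation definition across 9.1, 9.2.2, 9.3 and 9.3.2.1, settling whether COPD must be the primary diagnosis, may be in any position, or need not be coded.
2. Before outcome analysis, prespecify a sensitivity analysis of the primary Cox model, reported beside the main hazard ratio. In it, a qualifying event with a pneumonia code on the encounter, or on any encounter within ±7 days, is not counted as an exacerbation. Use the full 9.3.2.2 code list, so that the primary and secondary outcomes share one definition of pneumonia.
3. State whether such a pneumonia event censors follow-up or the patient stays at risk, and whether the flag is applied before or after events within 14 days are merged.
4. Report, by arm, the share of first exacerbations carrying a pneumonia code. This supplies an observed counterpart to p.

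The cost is protocol wording and one flag on claims already held. The sensitivity analysis will have fewer events and may over-correct, so both hazard ratios should be shown and the primary analysis can stay.
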